#### **12.4 Intensity / Severity**

Regarding the intensity/severity of each AE, the investigator will assess and evaluate the relationship according to the following definitions:

**Table 3. Adverse Event Intensity / Severity Definitions**

Mild	Awareness of signs, symptoms, or events that are otherwise easily tolerated that may result in minimal transient impairment of a body function or damage to a body structure, but do not require intervention other than monitoring.
Moderate	Any event that results in moderate transient impairment of a body function or damage to a body structure that causes interference with usual activities, or that warrants possible intervention, such as the administration of medication, to prevent permanent impairment of a body function or damage to a body structure.
Severe	Any event that is incapacitating (an inability to do usual activities) or is life-threatening and results in permanent impairment of a body function or damage to a body structure, or requires intervention, such as major surgery, to prevent permanent impairment of a body function or damage to a body structure.

## 12.5 Outcome

Regarding the outcome of each AE, the investigator will assess and evaluate the outcome according to the following classifications:

**Table 4. Adverse Event Outcome Classifications**

Classification	Definition
Resolved without sequelae	Subject fully recovered with no observable residual effects
Resolved with sequelae	Subject recovered with observable residual effects
Improved	Subject's condition improved, but residual effects remain
Unchanged	AE is ongoing
Worsened	Subject's overall condition worsened
Death	Subject died as a result of the AE

## 12.6 Adverse Event Reporting and Documentation Requirements

### 12.6.1 Adverse Event Reporting Requirements

**Investigator responsibilities:**

*Reporting by the Investigator to Biosense Webster:*

AE information will be collected throughout the study and will be recorded on the eCRFs by the study investigator and/or study coordinator. Each AE must be reported regardless of classification, seriousness, intensity, outcome or causality. All AEs will be monitored until they are adequately resolved or explained. Timing for reporting various AEs is described in Table 5.

**Table 5. AE Reporting Requirements and device return**

Type of Adverse Event*	Reporting Requirements for new and follow up information
Non-serious non related AE or non serious ADR	Report to Biosense Webster as soon as possible
Non-serious ADE***	Report to Biosense Webster as soon as possible
SAE	Report to Biosense Webster immediately but not later than 24 hours of awareness
USADE & SADE***	Report to Biosense Webster immediately but not later than 24 hours of awareness
Subject Death	Report to Biosense Webster immediately but not later than 24 hours of awareness
Study Device Deficiencies (failure/malfunction) associated with an AE***	Report both study device failure and AE to Biosense Webster immediately but not later than 24 hours of awareness
Study Device Deficiencies that might have led to a SAE**/***	Report study device failure to Biosense Webster immediately but not later than 24 hours of awareness
Study Device Deficiencies not associated with an AE***	Report study device failure to Biosense Webster immediately but not later than 24 hours of awareness
Other (concomitant) Device Deficiencies associated or not associated with an AE	Report to Biosense Webster as soon as possible per regular complaint process

\* Must be reported by eCRF (telephone, e-mail or fax transmission) to Biosense Webster by the study site personnel, whether or not it is deemed related to the study device, procedure, or drug.

\*\* Device deficiencies that could have led to serious adverse device effect if

- a) if either suitable action had not been taken,
- b) if intervention had not been made, or
- c) if circumstances had been less fortunate,

\*\*\* Devices need to be returned per Biosense Webster return procedure.

NOTE: Complaints related to products manufactured and/or distributed by Biosense Webster, used during the procedure related to other devices (other than the study device under investigation), are to be reported according to current Biosense Webster procedures and other policies as necessary (i.e., institutional policies, EC / EB [or equivalent] policies, and local regulations), investigators are instructed to return devices in accordance with current company procedures and other relevant regulations.

NOTE: Complaints related to non-Biosense Webster, Inc. products must be handled according to institutional policies, EC / EB (or equivalent) policies, and local regulations.

*Reporting by Investigator to EC/national CA*

The Investigator will report events to the EC / EB (or equivalent) as well as to the appropriate authorities (e.g., competent authorities) according to the prevailing regulations per country and/or site.

### **Biosense Webster responsibilities:**

The sponsor shall keep detailed records of all adverse events relating to the study which are reported to him by the investigators.

#### **Expedited reporting**

##### *General*

Biosense Webster shall report all reportable events occurred throughout the study to relevant participating CA's. ECs / EBs will receive events only occurred in subjects, recruited in their own country, unless more stringent national regulations are applicable.

##### *Device/procedure related events and device deficiencies*

In accordance with 21 CFR 812 (Subpart C), 803, ISO 14155, MDD 93/93/42/EC, Meddev 2.12/1, any malfunction or deterioration in the characteristics and/or performance of a device, as well as any inadequacy in the labeling or the instructions for use which, directly or indirectly, might have led to or might have led to the death of a patient, or user or of other persons or to a serious deterioration in their state of health, will be considered for reporting by Biosense Webster to the appropriate authorities (e.g., competent authorities) as well as to the ECs / EB (or equivalent) according to the prevailing regulations per country. For countries outside Europe, Biosense Webster adheres to Medical device vigilance requirements per national regulations.

#### **Annual reporting**

Biosense Webster shall perform annual safety reporting to the appropriate authorities (e.g., competent authorities), ECs / EBs (or equivalent) as well to Investigators according to the prevailing regulations per country.

### **12.6.2 Adverse Event Documentation**

The investigator is responsible for ensuring that all AEs observed by the investigator or reported by the subject that occur from the time that the subject has signed the informed consent through the end of the study are properly assessed, recorded, and reported as defined and described in the Adverse Events section of this protocol. All AEs must be assessed by the study investigator and properly documented by completing the subject's medical records (source documents) and appropriate eCRF. Additional documentation may be requested by Biosense Webster, including but not limited to, a written subject narrative detailing the clinical course of the AE, a copy of any correspondence with the local EC, and extracts from medical records.

### **12.6.3 Serious Adverse Event Documentation**

Subjects experiencing a SAE must be examined by a physician or qualified health care professional as soon as possible. The physician in attendance will do whatever is medically needed for the safety and well-being of the subject. The subject will remain under observation as long as medically indicated. All SAEs will be followed until resolution or until the event stabilizes according to the medical judgment of the investigator.

All efforts shall be put in place, by the investigator, to collect SAE-related documentation (e.g., eCRFs, subject's discharge summary) as soon as possible after initial notification of the event to Biosense Webster. Additional information shall be reported immediately but no later than 24 hours to Biosense Webster. Follow-up reports relative to the subject's subsequent course must be submitted to Biosense Webster or designee until the event has resolved or, in case of permanent impairment, until the condition stabilizes.

Documentation related to the SAE (e.g., additional laboratory tests, consultation reports, post-mortem reports, new information relating to a previously reported SAE, etc) will be provided

by the investigator to Biosense Webster or designee in a timely manner, when requested. If the subject is withdrawn from the study because of the SAE, the information must be included on the appropriate eCRFs.

## 13.0 Statistical Analysis

### 13.1 Clinical Study Objective

The objective of this study is to determine whether early RF ablation treatment, using the CARTO® 3, CARTO® XP or CARTO® RMT System and THERMOCOOL® Catheter Family in subjects with PAF, delays progression of AF compared with drug therapy (either rate or rhythm control) using current AF management guidelines.

### 13.2 Primary Endpoint

Time to persistent AF/AT (excluding isthmus-dependent atrial flutter) at 3 years will be used to measure the primary endpoint. Persistent AF/AT is defined as AF lasting longer than 7 consecutive days or requiring termination by cardioversion after 48 hours.

### 13.3 Overview of Statistical Methodology

Adaptive group sequential survival design is used in this study to examine the primary endpoint. The primary endpoint will be analyzed using the Kaplan-Meier (KM) method and account for censored observations following the intent-to-treat principle. Group sequential method, multiple interim examinations of the primary endpoint using alpha spending functions and conditional power, will be performed at regular time intervals during the course of the trial to determine whether the study will be stopped early for effectiveness or futility. In addition, sample size re-estimation will be used to provide a chance to increase the sample size close to the end of the enrollment if the study is still promising but underpowered due to uncertainties regarding the effect size and cross-over rate.

### 13.4 Sample Size and Power Calculation

A total sample size of 322 (161:161) subjects will be required to ensure 85% power to detect the effect size measured by negative log of the hazard ratio equal to 1.154f (treatment group over control group). This calculation assumes a 50% cross-over rate from the AAD group to the ablation group, a 10% drop-out rate in each group over the 3 year follow-up period, and 1.5 years accrual time. This calculation is based upon one-sided superiority testing with alpha equal to 0.025. Using meta-analysis, the rates of disease progression at the end of follow-up are estimated to be 25% and 5% in the AAD and ablation group, respectively (see the point estimate justification document for details, Appendix C). The sample size calculation is based upon the method developed by Rubinstein, Gail and Santner (RGS,1981) and also incorporates group sequential design with multiple interim looks.

#### Adaptive Sample Size Re-estimation:

Due to the uncertainties associated with the cross-over rate and the effect size, the sample size will be reestimated 1.5 years after the start of enrollment or at the end of the enrollment

---

$$^f -\log_e \left( \frac{\hat{\lambda}_t}{\hat{\lambda}_c} \right) = -\log_e \left( \left( -\frac{\log_e(0.95)}{3} \right) / \left( -\frac{\log_e(0.85)}{3} \right) \right) = 1.154$$

whichever occurs earlier. Conditional power (CP) will be calculated at that time to determine how promising the interim results are. CP is defined as the conditional probability that the final result will exceed a critical value given the data observed thus far, and an assumption about the trend to be observed in the remainder of the study. If the CP is less than 0.3, then the study is considered not promising and the sample size will not be increased. If the CP is greater than 0.9, then the study is deemed fully powered and the sample size will not be increased. If the CP falls in the promising zone (0.3-0.9), the sample size will be reestimated based upon the observed effect size and the CHW (Cui, Hung and Wang). Adaptive Method will be used for statistical testing.

### 13.5 Randomization

Subject randomization will be 1:1 between catheter ablation and AAD therapy. The randomized block design, stratified by gender and site, will be used to ensure a gender balance by treatment group at each site. Adaptive randomization will also be executed to further ensure the allocation balance of treatment groups by gender at each site. Subjects will be randomized in the order of their enrollment. If a randomization assignment is inadvertently disclosed prior to use, the assignment will never be used.

### 13.6 Analysis Populations

The study contains two treatment arms with subjects receiving either catheter ablation, with or without AAD therapy; or, AAD therapy alone. The following analysis populations will be used to complete the analyses of data:

**Intent to treat subject population (ITT):** The ITT subject population will include all subjects randomized, where subjects will be classified by the group to which they are randomized, regardless of the treatment received. For the ITT population, cross-over subjects will be included in the Control Group per randomization. Lost-to-follow-up and withdrawn / early termination subjects will also be included in the ITT population.

**Per protocol subject population (PP):** The PP subject population will include randomized subjects who satisfy the following criteria, according to the treatment actually received:

- **Test Group:** subjects who
  - have undergone RF ablation,
  - are treated with the study catheter (THERMOCOOL® Catheter Family)
  - are in compliance (no major protocol deviations) with the study protocol, and
  - have been treated for the study-related arrhythmia.
- **Control Group:** subjects who
  - have started an investigator-prescribed AAD and completed the dose-loading period (2 weeks),
  - have not undergone RF ablation,
  - are in compliance (no major protocol deviations) with the study protocol, and
  - have been treated for the study-related arrhythmia.

The analyses conducted in the PP population will be as treated analyses. Subjects who have undergone RF ablation will be included in the Test Group regardless of the original treatment assigned (original randomization). Thus, cross-over subjects will be included in the Test Group for PP analyses.

**Safety Population (SP):** The SP will include all subjects who have undergone insertion of an ablation catheter, either as Test Group or cross-over subjects; and, subjects who started an

investigator-prescribed AAD in the Control Group and did not initiate ablation therapy. Analysis of catheter-related complications will be limited to include only subjects who initiated ablation treatment (catheter insertion) - Test Group and cross-over subjects. Adverse drug reactions will be analysed overall for all the subjects who have taken investigator-prescribed AAD and analyzed separately for cross-over subjects, those in the Test and Control Groups (excluding cross-over patients).

The primary effectiveness analysis will be conducted in the ITT population. Secondary effectiveness analyses will be performed in the PP population. All safety data analyses will be performed in the SP.

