Persistent AF/AT	AF/AT which is sustained beyond seven days; or, lasting more than 48 hours and less than seven days but necessitating pharmacologic or electrical cardioversion.
Long-standing persistent AF/AT	Continuous AF of greater than one-year duration.
AF episode	An episode of AF > 30 seconds. Atrial fibrillation and atrial flutter (including atypical flutter) are considered episodes of AF. Atrial flutter alone is not considered an episode of AF.
Complete PVI	Entrance block confirmed with or without the use of a focal catheter.
Procedure time	Time from introduction of first catheter to withdrawal of last catheter (minutes).

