The risk of pulmonary AEs (e.g., pulmonary vein stenosis, thrombus and hypertension), associated with an AF ablation procedure targeting the pulmonary veins, is considered small (<4%).

Other potential complications, which may result from catheter insertion and manipulation as part of the prerequisite electrophysiology study and mapping procedure, include:

- Allergic reaction to the local anesthetic, sedatives, x-ray dye, heparin, protamine, or other agents administered during the procedure (risk <1%).
- Arterial or venous injury, including arterial dissection, thrombosis, occlusion or hemorrhage at the catheter insertion sites or at other sites along the vessels (risk <1%). This may produce hemorrhage, hematoma or ischemic injury to an extremity or major organ.
- Hemorrhage as a result of anticoagulation (risk <0.5%), which may require transfusion.
- Infection, either at the catheter insertion site or systemically, including endocarditis and septic emboli (risk <0.5%). This risk can be minimized by using standard aseptic technique and by the use of antibiotic agents when indicated.

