Safety Population: The Safety Population will include all subjects who have undergone insertion of an ablation catheter, either as Test Group or cross-over subjects; and, subjects who started an investigator-prescribed AAD in the Control Group and did not initiate ablation therapy. Analysis of catheter-related complications will be limited to include only subjects who initiated ablation treatment (catheter insertion) either as Test Group and cross-over subjects.

Adverse drug reactions will be analyzed overall for all the subjects who have taken investigator-prescribed AAD and analyzed separately for cross-over subjects, those in the Test and Control Groups (excluding cross-over subjects).

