9.4 Study Treatment

The study treatments will be summarized according to the following features:

- Number of subjects in Control group with crossover to a RF ablation
- First ablation procedure (index ablation procedure in test group)
 - Anticoagulation strategy
 - Catheter used
 - Ablation catheter inserted (Y/N)
 - RF ablation performed (Y/N)
 - Heart rhythm at start
 - PV ablation (Y/N)
 - RF energy delivery time
 - Ablation outcome (complete PVI achieved: Y/N, entrance block confirmed: Y/N, sinus rhythm at the end of the procedure: Y/N, electrical cardioversion at the end of the procedure: Y/N, sinus rhythm post electrical cardioversion: Y/N)
- Baseline Medication regimen (same as pre-study, new) (drug therapy group only)
- Cardiovascular Medication (see below)

Summaries of Cardiovascular Medication: Cardiovascular Medication will be coded using the WHO Drug Dictionary (September 2011 or newer). Incidences of cardiovascular medications will be summarized by ATC level 2 and ATC level 4, if

applicable, and by treatment group, unless otherwise specified. The following summaries of incidences will be prepared including test and control group:

- Cardiovascular medication at baseline: All cardiovascular medication which was started before/at date of randomization and was not discontinued before/at date of randomization will be included in this summary.
- Cardiovascular medication started after baseline: All cardiovascular medication which was started after date of randomization will be included in this summary. This may include dose changes after baseline if these are recorded as new medication entries.
- Concomitant cardiovascular medication: All cardiovascular medication which was started at any time during study and was not discontinued before/at date of randomization will be included in this summary.

In case start and/or end date are incomplete, a medication will be analyzed as concomitant medication as long as it cannot definitely be shown that the medication was discontinued before date of randomization. For concomitant medications, in case it cannot unequivocally be decided if the medication started before or after baseline, these will be analyzed as baseline medication, but excluded from medication started after baseline.

Additionally to these general medication summaries, summaries of new AADs started after baseline will be prepared as described in section 10.6.2).

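### A Test subject whose ablation procedure is started but stopped for good before the ablation catheter is inserted appears in no aggregate safety table

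*Protocol*

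**What the plan says.** Protocol 13.6 defines two routes into the Safety Population. The ablation route reads: "The SP will include all subjects who have undergone insertion of an ablation catheter, either as Test Group or cross-over subjects". The drug route is for subjects who started an "investigator-prescribed AAD in the Control Group and did not initiate ablation therapy". SAP section 7 repeats both, the first as: "The Safety Population will include all subjects who have undergone insertion of an ablation catheter, either as Test Group or cross-over subjects". Both documents treat initiating ablation treatment as meaning catheter insertion.

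The scope is complete. Protocol 13.6 says: "All safety data analyses will be performed in the SP". SAP section 11 puts all safety endpoints on the same population, and SAP 15.1 assigns every table in the 14.3 series to it. The index-procedure tables (14.1.8.1 to 14.1.8.4) also use it.

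Protocol 9.5 classes a Test subject who never has the THERMOCOOL ablation catheter inserted as excluded. SAP 9.4 nevertheless plans a yes/no item on whether the ablation catheter was inserted, so procedures that stop short of insertion are foreseen.

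**The concern.** Membership of the ablation safety set depends on reaching a step that a serious early complication can prevent. That is exclusion on an outcome. The subjects who drop out of the tables for this reason are, by construction, those in whom something went wrong early.

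The protocol does regard harm around access and sedation as procedural harm. Appendix A lists reactions to sedatives and anaesthetic, and arterial or venous injury, among complications "which may result from catheter insertion and manipulation as part of the prerequisite electrophysiology study and mapping procedure". Section 12.1.1 includes vascular access complications, pneumothorax and death among the primary AEs. Table 2 attributes to the procedure events linked to the standard electrophysiology or ablation procedure, not only those linked to the ablation catheter.

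At stake is the reported rate of procedural complications in an open-label comparison of ablation with drugs. A missing Test case lowers the ablation figure. A cross-over case stopped early moves from the ablation side to the Control column.

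**Working it through.** There is no figure in the plan to reproduce. The check is a reading of the definitions, followed by an illustration of size.

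**Step 1: who is in the set, and where the event goes.**

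| Subject | In Safety Population? | Where the event appears |
|---|---|---|
| Test, catheter inserted, RF delivered | Yes | Safety tables |
| Test, catheter inserted, no RF (discontinued, Protocol 9.5) | Yes | Safety tables |
| Test, procedure postponed, catheter inserted later | Yes | Safety tables; AEs are collected from consent (Protocol 12.6.2) |
| Test, procedure started, never inserted | No: fails the ablation route, and the drug route is for Control only | ITT listings only |
| Control on drug, cross-over procedure started, never inserted | Yes, by the drug route, since ablation was not initiated | Control column, including the procedure-causality table (14.3.3.3) |

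Only the last two rows are a problem.

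**Step 2: which tables are affected.** SAP 11.2 restricts catheter-related AEs to those possibly, probably or definitely related to the study device. An event before that device is inserted would rarely qualify, so that table loses little. The loss is in the procedure-related line of SAP 11.1, the serious AEs of SAP 11.3 and the primary AEs of SAP 11.4. It extends to the case listings numbered as tables 14.3.5.5 and 14.3.6.2, which are also on the Safety Population. In the 14.1.8 tables, no Test subject can appear as not inserted, because such a subject is not in the population.

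**Step 3: what remains.** SAP 15.2 places listings 16.2.15 (ablation procedures), 16.2.23 (AEs) and 16.2.24 (SAE forms) on ITT. The events stay on record but enter no rate.

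**Step 4: illustration of size.** The documents give no count of such events, so the counts here are assumed. Let N be attempted Test procedures, b complications among inserted subjects, and k complications that end the procedure before insertion.

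- Rate on all attempts = (b + k) / N
- Rate on the Safety Population = b / (N − k)
- Share not shown = 1 − [b / (N − k)] / [(b + k) / N]

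With N = 161, the planned Test Group in Protocol 13.4:

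| b | k | All attempts | Safety Population | Share not shown |
|---|---|---|---|---|
| 3 | 1 | 4/161 = 2.48% | 3/160 = 1.88% | 25% |
| 3 | 2 | 5/161 = 3.11% | 3/159 = 1.89% | 39% |
| 3 | 3 | 6/161 = 3.73% | 3/158 = 1.90% | 49% |
| 6 | 1 | 7/161 = 4.35% | 6/160 = 3.75% | 14% |
| 6 | 2 | 8/161 = 4.97% | 6/159 = 3.77% | 24% |
| 6 | 3 | 9/161 = 5.59% | 6/158 = 3.80% | 32% |

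If k = 0 nothing is lost. N almost cancels, so the share is close to k / (b + k) and does not rest on the planned sample size. That matters because SAP 5.1 says the study ended early.

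**The case against.** The strongest reply is that the gap is narrow and that several wider readings fail. Most of this stands.

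- A reader might infer that harm is counted only from the moment of insertion. The rule selects subjects, not event times. For anyone ever inserted, no text drops earlier events.
- A reader might infer that the catheter-related complication endpoint is understated. That endpoint requires relation to the device, so an insertion-based denominator suits it.
- A reader might infer that the events vanish. They do not: the ITT listings hold them, listing 16.2.23 is also an interim output, and exclusions are listed with reasons (SAP 9.1).
- A reader might infer that an aborted cross-over raises the adverse drug reaction rate. SAP 11.5 requires relation to the AAD, so it would not.
- A reader might infer that all electrophysiology study and mapping harm precedes insertion. Protocol 9.5 describes discontinued Test subjects who already have the catheter in when a non-study arrhythmia is found at electrophysiologic study, and they are in the set. Transseptal puncture is not named in either document.
- Safety is descriptive, with no between-group safety test to be biased.

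What the reply does not answer is the core gap. A line in a listing does not enter a reported rate, and no section brings a started procedure without insertion back into a Test Group safety table.

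**Conclusion.** The gap is real and limited. It covers Test subjects whose procedure was started and never reached insertion, who are missing from every aggregate safety table. It also covers Control subjects whose cross-over stopped at the same stage, whose event is placed in the Control column but remains identifiable as procedural. Following the plan as written can understate procedural harm from ablation.

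The size is unknown. It would be tempting to add up the separate below-1% risks in Appendix A and assume that some fraction occur before insertion. Those figures are upper bounds, the documents give no such fraction, and the resulting understatement would simply restate the fraction chosen. What can be said is conditional: with 3 or 6 complications tabulated, one missing case lowers the rate by about 0.6 percentage points, which is 25% or 14% of it.

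This is worth correcting as a cheap improvement. It does not touch the primary effectiveness analysis.

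**What to change.** In Protocol 13.6 and SAP section 7, define an additional set of all subjects in whom an ablation procedure was started, index or cross-over. Take the start as procedural sedation or first vascular access. Pre-procedure TEE is a poor start point: it would bring in subjects who had imaging only, and Table 1 schedules it only for those randomized to PVI.

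Use this set for the procedure-related, primary-AE, serious-AE and procedure-data tables, and show ablation catheter not inserted as a row. Keep the insertion-based denominator for catheter-related AEs. If changing the population is unwelcome, add one table of AEs in all attempted procedures, with and without insertion.

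AEs are already collected from consent and the insertion item is already planned. SAP 9.4 does not show a field for sedation or first puncture, so a small derivation is needed to identify started procedures. This assumes that a procedure record was completed for those that were stopped. The remaining costs are a few more subjects in the denominator and a complication rate that may be slightly less favourable.
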